**Table 26: Magnitude of Difference in Responses Detectable with 80% Power**

Response Proportion in the Placebo Group	Response Proportion in the Vaccinated Group	Difference
0.05	0.52	0.47
0.1	0.59	0.49
0.15	0.65	0.50
0.2	0.71	0.51
0.5	0.95	0.45

**Figure 5: Power Curves for Assessment of Vaccine Virus Shedding in RSV Seronegative Vaccinees**

With a sample size of 20 seronegative vaccine recipients, the 90% CI around a sample mean peak titer of  $2.5 \log_{10}$ , with a SD of 1.5 (from IMPAACT 2000) is (1.92, 3.08). This ensures with 90%

confidence that the true population mean peak titer is between 1.92 and 3.08  $\log_{10}$ , and with 95% confidence that the true population mean is not lower than 1.92  $\log_{10}$ .

With the same sample size of 20, the 90% CI around a proportion of 18/20 (90%) vaccine recipients who shed vaccine virus is (72%-98%). For a proportion of 19/20 (95%) the 90% CI is (78%-99.7%), and for 20/20 (100%) the 90% CI is (86%-100%). For the target proportion of 95%, this ensures with 95% confidence that the true proportion of vaccine recipients who shed vaccine virus is not lower than 78%.

## 9.4 MONITORING

### 9.4.1 Site Monitoring Plan

As per International Conference on Harmonisation Good Clinical Practice (ICH-GCP) 5.18 and FDA 21 CFR 312.50, clinical protocols are required to be adequately monitored by the study sponsor. This study monitoring will be conducted according to the “NIAID Intramural Clinical Monitoring Guidelines.” Monitors under contract to the NIAID/OCRPRO will visit the clinical research site to monitor aspects of the study in accordance with the appropriate regulations and the approved protocol. The objectives of a monitoring visit will be: 1) to verify the existence of signed informed consent documents and documentation of the ICF process for each monitored subject; 2) to verify the prompt and accurate recording of all monitored data points, and prompt reporting of all SAEs; 3) to compare CRIMSON data abstracts with individual subjects’ records and source documents (subjects’ charts, laboratory analyses and test results, physicians’ progress notes, nurses’ notes, and any other relevant original subject information); and 4) to help ensure investigators are in compliance with the protocol. The monitors also will inspect the clinical site regulatory files to ensure that regulatory requirements (Office for Human Research Protections, OHRP), FDA, and applicable guidelines (ICH-GCP) are being followed. During the monitoring visits, the investigator (and/or designee) and other study personnel will be available to discuss the study progress and monitoring visit.

The investigator (and/or designee) will make study documents (e.g., consent forms, CRIMSON data abstracts) and pertinent hospital or clinical records readily available for inspection by the local IRB, the FDA, the site monitors, and the NIAID staff for confirmation of the study data.

A specific protocol monitoring plan will be discussed with the PI and study staff prior to enrollment. The plan will outline the frequency of monitoring visits based on such factors as study enrollment, data collection status and regulatory obligations.

### 9.4.2 Monitoring by the NIAID Intramural Data and Safety Monitoring Board

The NIAID Intramural DSMB is constituted to review the safety data of Intramural NIAID clinical studies that require DSMB oversight. The NIAID Intramural DSMB includes independent experts in infectious diseases, biostatistics, and clinical research that do not have direct involvement in the conduct of the study and have no significant conflicts of interests as defined by NIAID policy. The DSMB will review the protocol prior to opening the study to enrollment. The DSMB will meet at least twice a year or on a schedule specified by the DSMB to review the completeness of the study data, the adherence to the protocol, and AE data.

Cumulative safety data (pooled across arms, with the vaccine and placebo arms presented together) will be submitted to the DSMB Executive Secretary for DSMB review. The DSMB Executive Secretary will provide the PI with DSMB recommendations promptly, and the official DSMB Report will then be provided in a timely fashion through the office of the NIAID Clinical

Director. The PI will submit the written DSMB recommendations to the IRB upon receipt. All SAEs, LRIs, UPs and IND safety reports will be reported by the PI to the DSMB at the same time that they are submitted to the IRB and/or regulatory sponsor (OCRPRO). The PI will notify the DSMB of any cases of intentional or unintentional unblinding as soon as possible. The PI will notify the Board at the time a pausing or halting criteria are met and obtain a recommendation concerning continuation, modification, or termination of the study.

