# **2 OBJECTIVES**

## **2.1 PRIMARY OBJECTIVES**

### *Safety*

1. To assess the frequency and severity of study product-related solicited and unsolicited AEs in RSV-seropositive participants (group 1) from day 0 through the 10th day following inoculation
2. To assess the frequency and severity of study product-related solicited and unsolicited AEs in RSV-seronegative participants (group 2) from day 0 through the 28th day following inoculation
3. To assess study product-related serious adverse events (SAEs) in RSV-seropositive participants (group 1) from day 0 through the 28th day following inoculation
4. To assess study product-related SAEs in RSV-seronegative participants (group 2) from day 0 through the 56th day following inoculation

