## **3 STUDY DESIGN**

The study will be double-blind, randomized, and placebo-controlled. Participants in groups 1 and 2 will be block-randomized in groups of 3 at a ratio of 2:1 to receive vaccine or placebo, respectively. The vaccine will be evaluated in a stepwise fashion beginning with RSV-seropositive children (Group 1) and proceeding sequentially in RSV-seronegative children (Group 2). For the purpose of this study, RSV-seropositive is defined as having a serum neutralizing antibody titer of  $\geq 1:40$ , and RSV-seronegative is defined as having a serum neutralizing antibody titer of  $< 1:40$ . This definition has been used in previous evaluations of live-attenuated RSV vaccines (11, 24, 35). In these previous studies, live-attenuated RSV vaccines were highly restricted in replication and poorly immunogenic in children with titers  $\geq 1:40$  but were far less restricted in replication and highly immunogenic in children with titers  $< 1:40$ . These data suggest that this neutralizing antibody cutoff can distinguish effectively between RSV-experienced and RSV-naïve children.

The study will proceed to group 2 if there are not more than 2 vaccine-associated solicited AEs and no vaccine-associated LRIs in RSV-seropositive children. If 3 or more RSV-seropositive children have respiratory or febrile illness that coincides with shedding of  $> 10^{2.5}$  PFU of vaccine virus as detected by culture, then we will enroll an additional 15 RSV-seropositive children to continue evaluating the safety, infectivity, and immunogenicity of the vaccine virus.

Enrollment occurs at the time of inoculation with study product, Day 0, and will occur between April 1 and October 31 to avoid the time during which wt RSV typically circulates in the community ([Appendix V](#), Figure 6). Accrual will stop prior to November 1.

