## 4 STUDY POPULATION

Approximately 15 RSV-seropositive children  $\geq$  12 months to  $<$  60 months of age will be enrolled; 10 will receive a single dose of  $10^{5.7}$  PFU of vaccine and 5 will receive a single dose of placebo. Subsequently, 21 to 30 RSV-seronegative infants and children  $\geq$  6 months to  $<$  25 months of age will be enrolled in the study and will receive a single dose of either  $10^{5.0}$  PFU of vaccine or placebo in a 2:1 ratio. These numbers were chosen based upon experience with phase I evaluation of other live-attenuated respiratory virus candidate vaccines ([11,23,25](#)) and statistical considerations (Section 9).

Placebo recipients are needed in pediatric studies to distinguish the background respiratory and febrile illnesses that occur in infants and children from those attributable to study vaccine. These numbers were chosen based upon experience with phase I evaluation of other live-attenuated respiratory virus candidate vaccines ([11,23,25](#)) and statistical considerations (Section 9).

Infants and children will be selected for participation according to the described study-specific co-enrollment considerations; the recruitment, screening, and enrollment process; and participant retention and withdrawal or termination.

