## **5.7 STUDY PRODUCT ACCOUNTABILITY**

The unblinded dispenser is responsible for maintaining an accurate inventory and accountability record of study-product and Lactated Ringer's Solution for Injection, USP for this study. A copy of the randomization code will be retained by the unblinded dispenser as outlined in the MOP. Without written request to unblind, the randomization code may not be released. The unblinded dispenser will be responsible for maintaining the blind.

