### **6.3 RANDOMIZATION**

Randomization numbers will be assigned by the unblinded laboratory vaccine dispenser and will be forwarded to the Data Safety Monitoring Board (DSMB) Executive Secretary. Unblinded laboratory personnel will label the vaccine syringes with the study virus vaccine name, PI initials, study number, subject's randomization number, preparer and vaccine verifier's initials and expiration date and time. The vaccine administrator and verifier will initial the label and place the label in the subject's study chart. The vaccination time will be documented on the vaccine administration record (VAR). All syringes will be disposed of by the study staff following the enrollment visit. A copy of the VAR will be sent to the laboratory.

A copy of the randomization code will be retained by the unblinded dispenser in the laboratory where the vaccine is prepared. Without the PI's written request to unblind, the randomization code will not be released to the clinical staff until the acute monitoring phase is complete for each subject within the randomization group. Pediatric subjects will be block-randomized in groups of 3 (2 vaccinees and 1 placebo recipient per block); this allows for maintenance of the blind during each subject's acute monitoring phase but also provides early information regarding safety, which is appropriate and common practice for phase 1 respiratory virus vaccine studies (11,23,25). Detailed procedures for randomization and unblinding will be placed in the laboratory study binder.

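### Clinical staff may hold the randomization code before the primary SAE windows and season surveillance end, while the routine cumulative DSMB report is pooled across arms

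*Combined protocol and SAP*

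**What the plan says.** **Blinding.** Section 3: "The study will be double-blind, randomized, and placebo-controlled". It gives no date at which the blind ends. Section 6.3 provides that, unless the PI asks in writing for earlier unblinding, "the randomization code will not be released to the clinical staff until the acute monitoring phase is complete for each subject within the randomization group". Its reason is that blocks of three keep the blind through each child's "acute monitoring phase but also provides early information regarding safety", which it describes as usual in phase 1 trials of such vaccines. Section 5.7 states: "Without written request to unblind, the randomization code may not be released". It makes no exception for the end of the acute phase.

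**Outcomes.** The acute phase is Days 0-10 (group 1) or 0-28 (group 2). The primary safety objectives extend past it; for group 2: "To assess study product-related SAEs in RSV-seronegative participants (group 2) from day 0 through the 56th day following inoculation". For group 1 the SAE window ends on Day 28. Section 8.1 gives the relatedness judgement to the study clinician. Sections 2.2 and 9.2.2 add medically attended illness with wild-type RSV in group 2 vaccine and placebo recipients. Staff collect it by weekly contact from 1 November to 31 March.

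**DSMB.** Section 4 gives the purpose of the control arm: "Placebo recipients are needed in pediatric studies to distinguish the background respiratory and febrile illnesses that occur in infants and children". Section 9.4.2 then says: "Cumulative safety data (pooled across arms, with the vaccine and placebo arms presented together) will be submitted to the DSMB Executive Secretary". The same section sends individual SAEs, LRIs, unanticipated problems and IND safety reports to the board. Under Section 8.3, a pause event found to be in a vaccine recipient and meeting a stopping criterion is reviewed by the DSMB before enrollment resumes.

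**The concern.** The primary SAE outcome counts only events judged related to study product, so that judgement defines the endpoint. After the acute phase it may be made by staff who know the arm. The same staff may collect season illness, for which Table 20 drops the requirement to meet the Appendix IV definitions.

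The board charged with independent safety review receives routine tables in which the arms cannot be told apart. The comparison with placebo that Section 4 relies on is therefore missing from routine review. What is at stake is the credibility of late SAE attribution, and the board's ability to notice a shift in mild or moderate respiratory illness. Section 8.1.1 says that solicited events of this kind may be expected if the vaccine is insufficiently attenuated.

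**Working it through.** The plan states no figure for this point. The check compares windows and then illustrates pooling.

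**1. SAE-window days after the earliest release** (Sections 8.1.1, 9.2.1)

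| | Acute phase | SAE window | Days in window | Days after acute phase |
|---|---|---|---|---|
| Group 1 | 0-10 | 0-28 | 29 | 28 - 10 = 18 (18/29 = 62%) |
| Group 2 | 0-28 | 0-56 | 57 | 56 - 28 = 28 (28/57 = 49%) |

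These are maxima per child, because release waits for the last child in the randomization group to finish the acute phase. If that term means the block of three, most post-acute follow-up can be unblinded. If it means the whole study group, early enrollees may finish the window blinded, but the last ones would not.

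**2. Season days (group 2)**

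- 1 November to 31 March = 30 + 31 + 31 + 28 + 31 = 151 days (152 in a leap year).
- Inoculated on 3 October: the acute phase ends 28 days later, on 31 October. For children inoculated by then, no season day falls within their own acute phase.
- Inoculated on 31 October, the last allowed day: it ends on 28 November, so 28 of 151 season days fall within it.
- On the whole-group reading, and assuming group 2 is enrolled in one year, release is possible by 28 November at the latest. At least 151 - 28 = 123 season days follow it.

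**3. What reaches the DSMB outside the pooled report** (Sections 8.3, 9.4.2)

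- Individually: every SAE, LRI and unanticipated problem.
- For DSMB review once the arm is found to be vaccine: unexplained or possibly vaccine-caused SAEs; LRIs with vaccine shedding or without another explanation; Grade 4 fever, or other Grade 3-4 solicited events, with shedding.
- No individual trigger: Grade 1-2 URI or otitis media, and Grade 1-3 fever. The last stopping criterion covers patterns of symptoms, but it depends on the protocol team's judgement.

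**4. What pooling hides.** The arm sizes, 20 and 10, are the plan's maximum for group 2. The event counts are assumptions. Pooled rate = (vaccine events + placebo events)/30.

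| Vaccine | Placebo | Pooled | One-sided Fisher p |
|---|---|---|---|
| 8/20 (40%) | 4/10 (40%) | 12/30 (40%) | 0.66 |
| 10/20 (50%) | 2/10 (20%) | 12/30 (40%) | 0.12 |
| 11/20 (55%) | 1/10 (10%) | 12/30 (40%) | 0.021 |

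The third row would be notable by arm, yet the pooled line is the same in all three.

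**5. What a by-arm table could establish.** One-sided exact Fisher power at 5%, 20 v 10, is about 35% for true rates of 50% v 20% and about 72% for 55% v 10%. The plan's Table 26 agrees in direction: for placebo rates of 0.2 and 0.1 it needs differences of 0.51 and 0.49 for 80% power, against 0.30 and 0.45 here.

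**6. Code-release wording.** Section 5.7 requires a written request in all cases. Section 6.3 requires one only before the acute phase ends. The two do not match.

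**The case against.** A reader might infer that blinding is inverted, with site staff seeing arms and the DSMB seeing only pooled data. The documents do not support that. The board receives the safety-critical events one by one and reviews qualifying events in vaccinees knowing the arm. Group 1 also has its own gate on vaccine-associated solicited events and LRIs before group 2 opens.

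Nor are most primary outcomes exposed. The solicited and unsolicited AE windows close with the acute phase. Section 6.10.2 assigns laboratory testing to personnel outside clinical assessment. SAE status follows defined criteria, and SAEs in the window are recorded whether or not judged related. Season illness is secondary, has no formal test, must be medically attended, and is tied to wild-type infection shown by laboratory testing.

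Section 6.3 sets an earliest release rather than requiring one, and gives a reason. The trial is first-in-human and exploratory. The documents do not say that families learn the arm, or that the randomization numbers sent to the DSMB Executive Secretary reveal treatment.

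All of this stands, and it narrows the point. It does not explain why the routine report is pooled, for which the plan gives no reason. Nor does early safety information require giving codes to the people who judge late SAEs: it could go to the DSMB and the sponsor medical monitor.

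**Conclusion.** The point holds in a limited form. Clinical staff may know the arm for up to 18 of 29 (group 1) or 28 of 57 (group 2) days of the primary SAE window, and for most or all of the RSV season. The relatedness of late SAEs is the primary judgement affected. Routine DSMB review cannot show an arm difference in non-serious respiratory or febrile illness that triggers no individual rule.

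The day counts assume release at the earliest permitted moment, and they depend on what randomization group means. The illness counts are illustrative. At 20 v 10 a by-arm table would display an excess but often not establish one. It does not follow that season-surveillance staff must stay blinded: the post-season visit can be as late as 30 September of the following year, and that delay is a debatable trade against the stated reason for early release. The change is worth making, but nothing here invalidates the design.

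**What to change.** 1. **Section 9.4.2.** Replace the pooled cumulative report with a closed DSMB report of solicited AEs, LRIs and SAEs by arm within each serostatus group, prepared by someone who already holds the code.
2. **Section 6.3.** Withhold codes from the clinical staff who judge SAE relatedness until the Day 28 visit (group 1) or Day 56 visit (group 2) is complete. Send early by-arm safety information to the DSMB and sponsor medical monitor. Keep case-level unblinding for pause events.
3. **Sections 5.7 and 6.3.** Reconcile the written-request requirement. State whether randomization group means the block of three or the whole study group, and say in Section 3 when the blind ends.
4. **Optional.** Keep season-surveillance staff blinded to the post-season visit, if the sponsor accepts the longer delay.

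Items 1-3 cost one extra closed table per DSMB review, wording changes, and a later look at the codes for the clinical team: about 18 days in group 1 and 28 in group 2, plus up to 7 more where the visit window is used. The LRI part of the group 1 gate already runs to Day 28, so item 2 adds little to that decision. The closed report gives up no blinding at the site.

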## **9.5 ANALYSES**

### **9.5.1 Assessment of Primary Objectives**

Safety data from all participants in CIR 322 who have been inoculated will be summarized together, including data from participants who discontinue study early or have some missed visits. In the immunogenicity analyses, those who do not provide data for the Day 28 Visit follow-up for RSV-seropositive participants and for the Day 56 Visit follow-up for RSV-seronegative participants (due to early discontinuation or missed visit) will be treated as “failures.” Sensitivity analyses will be performed to check if the results are consistent with those when these participants are excluded. Participants who receive any of the disallowed treatments listed in Section 5.10 during the first 28 days after inoculation for RSV-seropositive participants and during the first 56 days after inoculation for RSV-seronegative participants may be excluded from the immunogenicity evaluations after the time of the treatment. These participants, however, will be included in the safety evaluations for the duration of the study. These participants will not be replaced. Details of the analyses listed below will be included in the statistical analysis plan.

The frequency of solicited AEs and unsolicited AEs, along with 90% confidence intervals, during Study Days 0 to 10 in RSV-seropositive subjects and during Study Days 0 to 28 in RSV-seronegative subjects and of vaccine-related SAE during Study Days 0 to 28 in RSV-seropositive subjects and during Study Days 0 to 56 in RSV-seronegative subjects will be summarized. In addition, line listing of individual clinical solicited AEs and unsolicited AEs, graded by severity, will be prepared for events occurring during Study Days 0 to 10 in RSV-seropositive subjects and during Study Days 0 to 28 in RSV-seronegative subjects and vaccine-related SAE during Study Days 0 to 28 in RSV-seropositive subjects and during Study Days 0 to 56 in RSV-seronegative subjects.

The proportion of participants with infection defined as recovery of vaccine virus from a nasal wash as determined by culture and RT-PCR, and/or a  $\geq 4$ -fold rise in neutralizing antibody titer to RSV, will be summarized. A line listing of the individual peak titer of vaccine virus shed and duration of virus shedding in nasal washes by each individual will be prepared. In addition, the geometric mean peak titer and mean duration of virus shed will be provided for each treatment group.

The proportion of participants that develop 4-fold or greater rises in RSV-neutralizing antibody titer following vaccination will be summarized. A line listing of the individual RSV antibody titer pre- and post-vaccination will be prepared. In addition, the geometric mean and median antibody titers will be provided for each treatment group. Line listings of individual RSV-neutralizing antibody responses as well as of antibody responses to the RSV F glycoprotein will be prepared as well.

Where appropriate, a 1-tailed Wilcoxon rank sum test will be used to test the hypothesis that the vaccinated group will exhibit greater peak viral titers and antibody titers following vaccination compared to the placebo group. A 1-tailed Fisher’s exact test will be used to test the hypothesis

that the vaccinated group will exhibit a greater proportion of participants who develop fourfold or greater rises in RSV-neutralizing antibody titer following vaccination compared to the placebo group.

These will be the only formal statistical comparisons between the vaccinated and placebo groups. These tests will be carried out at a 5% significance level.

The study results will be compared with the criteria listed in Section 1.1 to determine if this vaccine is a promising candidate for further evaluation in expanded phase I studies or phase II studies.

